2 STUDY AIM AND OBJECTIVES

2.1 STUDY AIM

This project will investigate MPX vaccine uptake and real-world effectiveness in Australia.

2.2 PRIMARY OBJECTIVES

- 1. Determine the baseline prevalence of past MPX infection and the prospective incidence of MPX over 12 to 18 months of follow-up.
- 2. Determine vaccine effectiveness, adjusted for risk behaviour, measured separately for subcutaneous and intra-dermal routes, and separately for pre-exposure and post-exposure vaccination, and by time since vaccination.
- 3. Measure vaccine uptake and determine predictors of vaccine uptake.

2.3 SECONDARY OBJECTIVES

- 4. Measure predictors and severity of breakthrough infections after vaccination.
- 5. Identify under-vaccinated sub-populations to enable public health response.

3 STUDY DESIGN

3.1 SUMMARY OF STUDY DESIGN

To address the study objectives, this project will rapidly initiate an entirely online prospective observational study that will systematically survey participants each week for a minimum of 52 and up to 78 weeks to measure the short-term impacts of MPX and to detect trends throughout the MPX epidemic. Enrolment will occur for the first 6 months of the study period. If the epidemic is ongoing after 18 months, further follow-up may be considered. Participants will not be reimbursed for their participation, nor will their participation incur any expenses.

We will systematically follow individual participants each week for up to 18 months (12 months for those participants recruited at the end of month six). The weekly surveys will include questions on MPX testing, vaccination, and diagnosis, while also asking about sexual behaviours, including use of condoms and sexual positioning to determine any associations with the site of MPX infection. Each week, participants who indicate they have had a vaccination or positive diagnosis will answer additional questions, including severity of symptoms and location of infection.

Through the community-recruited sample, we will be able to identify uptake of MPX vaccines by age, sexual risk behaviours, and geographical coordinates (postcode). These data will allow us to identify subpopulations of under-vaccinated communities to inform targeted public health campaigns.

In consenting participants, data linkage will validate self-reported MPX infection and any significant adverse events to MPX infection and vaccination. Consent to data linkage is an optional component to the study.

3.2 AUTOMATED COHORT METHODOLOGY

Online, automated methodology enables person-specific study pathways to be executed based on each participant's unique history and real-time responses without researcher involvement.¹⁹ Development of this automated methodology was part-funded by the New South Wales Ministry of Health via the Prevention Research Support Program (PRSP). Leveraging existing infrastructure, this project is uniquely placed to monitor and detect trends in MPX infection and vaccine uptake and facilitates rapid monthly reporting. This proven methodology has been used to describe the rapid uptake of PrEP use following the widespread availability in Australia among a national sample of GBM between 2014 and 2019,^{20,21} and more recently has enabled the documentation of the impact the COVID-19 pandemic had on the use of HIV pre-exposure prophylaxis (PrEP).^{19,22} Ongoing automated weekly data collection since early 2020 has provided unique data in the short- and long-term impacts of the COVID-19 pandemic on HIV prevention and mental health,^{23,24} allowing for rapid monthly reporting to NSW Health of key trends.^{25,26}

3.2.1 STUDY DESIGN RATIONALE

As part of an ongoing cohort study of the impact of the COVID-19 pandemic among GBM, Co-PC [name] developed a world-first cohort-management system to automatically monitor, detect, and report data trends, and compare pre- and post-intervention scores in real-time, allowing for individually customised questionnaires.^{24,27}

Our cohort infrastructure enables person-specific study pathways to be executed based on each participant's unique history and real-time responses without researcher involvement, such as automatically disabling redundant questions for participants who previously indicated an infection or vaccination.

3.3 NUMBER OF PARTICIPANTS

To address the objectives relating to vaccine coverage, we require a minimum of 2,000 participants. The minimum number of participants needed to address the vaccine efficacy objective is 15,000 (at least 3,000 of whom should initially be unvaccinated). See section 9 for calculations.

The target population for this study is populations considered at high risk of MPX exposure as defined by the World Health Organization's (WHO) interim guidance on vaccines and immunisation for monkeypox.¹⁸ For the purpose of this study, this includes:

- All people (whether cis or trans men, cis or trans women, or non-binary) who
- Report sex with cis and trans gay, bisexual, and other males or non-binary people who have sex with cis or trans men (GBMSM+) in the preceding 12 months.

4 ENROLMENT OF PARTICIPANTS

4.1 ELIGIBILITY CRITERIA

Eligibility for this study has been adapted from the WHO interim guidance on vaccines and immunisation for monkeypox.¹⁸

4.1.1 INCLUSION CRITERIA

All inclusion criteria must be met to participate in the study.

- Age 18 years or older.
- All people (whether cis or trans men, cis or trans women, or non-binary) who
- Report sex with cis and trans gay, bisexual, and other males or non-binary people who have sex with cis or trans men (GBMSM+) in the preceding 12 months.
- Currently living in Australia.

4.2 STUDY PROMOTION

This study will enrol a community-recruited sample. We will use a wide range of digital platforms to reach a diverse sample of participants across Australia, including gay and bisexual geolocation dating apps such as Grindr[™] and Scruff[™], and social media sites such as Facebook[™], Instagram[™], and Twitter[™]. Social media advertisements will target participants living in Australia and whose profile activity reflects aspects of GBMSM+ identity.

Our community partner organisations will also promote the study through their dedicated social media networks and email newsletters. Advertisements and news stories may also be published on other websites with relevance to the target populations (e.g., websites of community partners and other GBMSM+, HIV, and trans and gender diverse organisations).

Participants of previous studies conducted in Australia and expressed interest to participate may also be invited to take part in this study.

Study information will also be distributed in NSW and Victorian sexual health clinics and MPX vaccination centres. Participants who attend clinics for NSW Health funded MPX vaccination will be offered participation at the site of vaccination. Each clinic will be provided with advertising material containing a unique QR code to allow us to determine where each participant was recruited. Local Health Districts will not be actively engaged in recruitment nor the consent process, and therefore we do not anticipate the need for site-specific approval. Regardless, we will submit an application for site-specific approval should it be required for the distribution to clinics of promotional material.

All recruitment advertisements will direct respondents to the study web page, which provides:

- The participant information sheet (available to read from the study website or download a PDF copy).
- A detailed description of the study aims.
- Requirements for participation.
- The time required for survey completion.
- Information about ethical approval.
- Study contact information.

Once the participant clicks on the "Enrol Now" button on the study website, they will be redirected to the online consent form where they will be screened for eligibility prior to providing consent. In a previous online cohort study, we successfully recruited 3,500 GBM through this method (HC14075 and HC200286).

Recruitment will commence until UNSW HREC and ACON provide approval.

4.3 ENROLMENT PROCESS

Enrolment, eligibility assessment, and consent is self-directed. Participants will be required to confirm their understanding of all study requirements, their willingness to participate in weekly surveys, and to provide an email address to receive weekly reminders to complete their survey. The database will automatically generate a deidentified participant ID and individualised link will remove the need for direct researcher contact. Participants can withdraw their consent from the study at any time via an automated link that will be included in all email communications.

4.4 PREVENTING DUPLICATED REGISTRATION

Participants' email addresses and mobile phone numbers collected at consent will act as a secondary ID code to prevent duplication of enrolment. The secondary ID is not available for access by any research staff. Rather, it automatically checks for duplications in the database, disabling people from registering with the same details. People, however, can register more than once using different email addresses and mobile numbers. As we have reduced the number of identifying information collected and will not be collecting system identifiers such as IP address, geolocation, or geographic coordinate, there is little control in preventing duplicated registrations using different details beyond what we have proposed. Since there is no monetary gain from participating in the study other than from automatically entering a weekly raffle, we anticipate no concern for duplicated registration. We base this assumption on our experience executing multiple studies using the same method across different populations,²⁸ research questions,²⁹⁻³¹ and internationally.³²

4.5 PARTICIPANT WITHDRAWAL

Participants will have the option to withdraw their consent at any point throughout the study. Details on how to withdraw from the study will be provided at the time of consent,

outlining a simple procedure and multiple means of withdrawal. Participants have two options to withdraw their consent:

- 1. Participants can contact the study team on the email provided in the consent form, or by replying to any email notification received requesting their consent be removed from the study.
- All email notifications sent to the participant will include a link to withdraw their consent. Each link contains the participant's unique, deidentified study identification number. By clicking this link, participants will be automatically redirected to a 'Withdraw consent from study' page and the database will automatically bring up the withdrawal page associated with their record (Figure 1).

FIGURE 1. AUTOMATED WITHDRAW CONSENT

Check below to withdraw from the study * must provide value		
\bigcirc Yes, please withdraw me from the study		
	Submit	

Participants simply click on their link and click Submit. A confirmation of withdrawal will be displayed to the participants.

FIGURE 1. AUTOMATED CONFIRMATION OF WITHDRAWAL

We're sorry to see you leave, but we thank you and appreciate your input into our study.

Our database has automatically withdrawn you from the study.

If you have any questions or would like to re-join the study,

Once submitted, all scheduled notifications are deleted, and all future communications are disabled. Error proofing programming prevents the withdrawn participants from receiving any future study notifications, including future extension, newsletters, and overrides their consent to be contacted for future research.

4.6 INCENTIVES TO PARTICIPATE

Participants will not be reimbursed for their participation, nor will their participation incur any expenses. To facilitate retention, participants can opt-in at the consent stage to be

eligible for weekly raffle prizes commencing at their second week of participation. Participants who complete their weekly questionnaire within 48 hours of initial invitation will enter a raffle to win one of four weekly prizes in the form of \$50.00 electronic gift cards. Winners will be randomly selected each week by STATA. Winners will be notified each Thursday by automatically sending a link for their gift cards to their nominated email or mobile number.

4.7 COMMUNICATION PLAN

4.7.1 Advertising

Online advertisements will consist of short messages that briefly describe the purpose of the study. Participation will be voluntary. To minimise potential biases and analyses, promotional material will contain a unique QR code to allow us to identify participants who heard about the study while receiving a vaccination at a NSW and Victorian sexual health clinic or other vaccination centre.

All recruitment advertisements will direct respondents to the study web page, which provides:

- The participant information sheet (available to read from the study website or download a PDF copy).
- A detailed description of the study aims.
- Requirements for participation.
- The time required for survey completion.
- Information about ethical approval.
- Study contact information.

Once the participant clicks on the "Enrol Now" button on the study website, they will be redirected to the online consent form where they will be screened for eligibility prior to providing consent.

5 STUDY ENDPOINTS

5.1 PRIMARY ENDPOINTS

- 1. Incidence of MPX among study participants, adjudged for risk behaviour.
- 2. Vaccine effectiveness, adjusted for risk behaviour, measured separately for subcutaneous and intra-dermal routes, and separately for pre-exposure and post-exposure vaccination.
- 3. Vaccine uptake and factors predictors of vaccine uptake.

5.2 SECONDARY ENDPOINTS

- 4. Incidence and predictors and severity of breakthrough infections after vaccination.
- 5. Identify factors of under-vaccinated sub-populations to enable public health response.

6 STUDY ASSESSMENTS AND FOLLOW-UP PROCEDURES

6.1 AUTOMATICALLY ASSESSING ELIGIBILITY

After reading the participant information sheet and when the participants click on the "Enrol Now" button, they will be redirected to the online consent form hosted on UNSW Sydney's REDCap database. Prior to assessing eligibility, participants will be asked to confirm they have read and understood the participant information sheet, understood the requirements of the study, and provide consent to proceed to assessing their eligibility.

Eligibility will be verified automatically through REDCap without the involvement of the research team to further protect participant confidentiality.³³ If participants are not eligible, they will not be able to register into the study nor provide any identifying information. Those considered ineligible will be automatically provided an explanation as to why they do not meet the study criteria and provided contact details for the study should they wish to discuss further. Reason(s) for ineligibility will automatically be displayed on the criteria the participant does not meet. See Figure 2 for an example of a participant not meeting the criteria.

FIGURE 2. NOTIFICATION OF INELIGIBILITY TO PARTICIPATE IN STUDY.

Close	curvov
Close	survey

Thank you for your interest in the TraX study. Unfortunately, you do not meet the eligibility requirements to participate. To participate in this study, you must:

- · Be at least 18 years of age.
- · Reported sex with gay, bisexual, or other men who have sex with men in the preceding 12 months (includes cis or trans gay, bisexual, and other men who have sex with men; trans or cis women; and non-binary people.
- Currently living in Australia.

If you would like to discuss this with our study team, don't hesitate to get in touch with us at [contact]

Participants who meet the eligibility requirements will proceed to providing consent.

6.2 INFORMED CONSENT PROCESS

Consent will be sought from all participants. Participants who meet the eligibility requirements will be progressed to an e-Consent form embedded within REDCap. Participants will consent on enrolment to complete weekly surveys. They will not be required to reconsent at every data-collection round. Identifying information, such as given name and date of birth is not a requirement to participate in the study. This online consent process is appropriate for our data collection method and participant group as this is an entirely online cohort study. Participants are required to provide an email address and have the option to provide a mobile number to allow text message notifications. On completion, participants will receive a locked PDF copy of their consent form via their nominated email account.

All recruitment advertisements will be directed to the study website which provides a detailed description of the study aims, inclusion criteria, requirements for participation, information about ethical approval, and study contact information. Participants will be provided with the Participant Information Statement and Consent Form (PISCF) through the study webpage and have the option to download a PDF. Participants will be asked to read the PISCF before consenting and to contact the researcher(s) if they have any questions.

6.2.1 VERIFYING ENROLMENT

We will implement a verification process following participants decision to consent in the research to check and authenticate email addresses and mobile numbers. A verification process ensures the details entered are from an authentic participant and that we have connected to the email address and mobile number owners.

Upon completing their consent, participants will receive an email or text message asking them to click a link to verify their registration. By clicking the link, their registration is verified, and the automatic study process for this participant is activated. If the link is not clicked, they will receive one reminder. Failure to verify their registration following the reminder will automatically terminate their record, and all data will be permanently deleted.

6.3 OPTIONAL CONSENTS

Participants will be invited to provide optional consents for additional aspects of the study.

6.3.1 DATA LINKAGE

We will seek consent to link data with commonwealth and state agency health and diseaserelated registries and databases and obtain state-based Population and Health Services Research Ethics Committee approval to conduct data linkage. Such registries include the Australian Immunisation Register, MPX, HIV, and sexually transmissible infections (STI) registries. This information will allow calculating the rates of MPX, HIV and STI diagnoses in the study. Further approval via a modification request will be sought prior to commencing data linkage. We will collect additional identifying information needed for data linkage from participants who provide consent. These identifiers include full name, date of birth, postcode of residence, and Medicare number (if available).

6.3.2 CONSENT TO BE CONTACTED TO PARTICIPATE IN FUTURE STUDIES

Participants can also provide consent to be contacted to participate in embedded studies. These studies may include providing biological samples and clinical data at or around the time of vaccination and MPX diagnosis, will each be the subject of separate ethics approvals., and will run in parallel to this project. This approach will enable us to target, assess eligibility automatically, and invite participants into new clinical studies being administered by the Kirby Institute.

6.4 BASELINE

Newly enrolled participants will complete a brief baseline questionnaire after completing their first weekly response (approx. 10-15 minutes to complete). The baseline survey will collect demographic characteristics, HIV status, MPX awareness and vaccine history. Baseline items will also include a brief measure of attitudes towards vaccines, as this will be an important indicator determining the likelihood of refusing a vaccination.

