6.5 WEEKLY QUESTIONNAIRE

The weekly questionnaire will take approximately 1 minute to complete depending on individual responses to items on sexual behaviour. Weekly questionnaire items include MPX testing, vaccination, diagnosis, and sexual behaviours.^{2,6,34-36}

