6.7 MPX- DIAGNOSIS

If a participant indicates a new positive MPX diagnosis in a weekly questionnaire, a disease severity and experience module will be enabled. Items included in this module were developed using data from the United States Centre for Disease Control and Prevention and the World Health Organization Global Clinical Data Platform Monkeypox Case Report Form.^{37,38} These items include information on symptoms, severity of infection, and type of vaccination. This will be enabled in the week of diagnosis, and then weekly for 4 more weeks to cover the disease period.

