9.3.2 VACCINE EFFICACY

- Disease incidence: Number of events observed (new MPXV infections) divided by total person years followed, presented as cases per 100 person-years.
- Vaccine efficacy: (incidence in unvaccinated incidence in vaccinated, divided by incidence unvaccinated)
- Multivariate: controlled for behaviour using Cox regression.

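### With baseline completed after the first weekly form and no entry cut-off, MPX already symptomatic or tested at entry can be counted as prospective incidence

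*Protocol*

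**What the plan says.** - **Two separate targets.** The first primary objective (Section 2.2) is: "Determine the baseline prevalence of past MPX infection and the prospective incidence of MPX over 12 to 18 months of follow-up".
- **Order of forms.** Section 6.4: "Newly enrolled participants will complete a brief baseline questionnaire after completing their first weekly response".
- **Weekly content.** Section 6.5: "Weekly questionnaire items include MPX testing, vaccination, diagnosis, and sexual behaviours". These questions therefore come before the baseline form.
- **Baseline content.** Section 6.4: "The baseline survey will collect demographic characteristics, HIV status, MPX awareness and vaccine history". It adds a measure of vaccine attitudes. The schedule of assessment in the synopsis, however, ticks MPX testing at baseline as well as weekly and six-monthly.
- **Eligibility.** Section 4.1.1: "All inclusion criteria must be met to participate in the study". The criteria cover age, sexual contact in the past 12 months and residence. None concerns current, suspected or past MPX.
- **Case trigger.** Section 6.7: "If a participant indicates a new positive MPX diagnosis in a weekly questionnaire, a disease severity and experience module will be enabled". The module is described as covering symptoms, severity and type of vaccination. No onset date or sample date is named.
- **Numerator.** Section 9.3.2: "Disease incidence: Number of events observed (new MPXV infections) divided by total person years followed". No entry cut-off is given.
- **Recruitment.** Section 4.2: "Study information will also be distributed in NSW and Victorian sexual health clinics and MPX vaccination centres". People attending for NSW Health funded vaccination are offered participation on site.

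**The concern.** The first objective depends on separating MPX present at entry from MPX arising during follow-up. Consider a person who is tested at a sexual health clinic, enrols the same day through the QR code, and receives a positive result before the first weekly form. They can report it there as a new diagnosis, which opens the case module. No study form has yet recorded their MPX history, and no stated rule assigns the case to baseline.

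Two primary estimates are exposed. Incidence may include cases that belong to prevalence. Vaccine effectiveness may also move, in a direction that depends on which group the misplaced cases fall in: it rises if they are mostly unvaccinated and falls if they are mostly people who enrolled at vaccination. In the second situation the cases would gather soon after vaccination and in the post-exposure group. Effectiveness by time since vaccination and effectiveness after exposure are both named in the second primary objective, and each rests on fewer events than the total.

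**Working it through.** **1. The protocol's planned events (Section 9.1.2, central row).** Inputs: 14,949 participants, 2,990 initially unvaccinated and 11,960 initially vaccinated; incidence 1 per 100 person-years in the unvaccinated; efficacy 70%; 80% of the unvaccinated vaccinated over 12 months; 56 events stated.

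Events = N × incidence × [a + (1 − a)(1 − VE)], where a is the unvaccinated share of person-time.

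- Linear switching: a = 0.2 × 0.6 = 0.12. Events = 149.49 × (0.12 + 0.88 × 0.3) = 57.4.
- Exponential switching: a = 0.099. Events = 55.2.

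Both are within 2 of the stated 56, so 56 is a fair yardstick.

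**2. Events by group, linear switching.**

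- Unvaccinated: 2,990 × 0.6 = 1,794 person-years, × 0.01 = 17.9 events.
- Vaccinated: 11,960 + 2,990 × 0.4 = 13,156 person-years, × 0.003 = 39.5 events.

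**3. Infections acquired before entry and diagnosed after it.** The protocol gives no infection-to-diagnosis interval; L = 1 to 3 weeks is assumed. Carry-in per group = number entering × rate × L/52.

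- Unvaccinated: 2,990 × 0.01 × L/52 = 0.58 to 1.73 cases.
- Vaccinated at their own rate: 11,960 × 0.003 × L/52 = 0.69 to 2.07. Total with the unvaccinated: 1.3 to 3.8, or 2% to 7% of 56.
- Vaccinated at the unvaccinated rate (as if all enrolled on the day of vaccination): 11,960 × 0.01 × L/52 = 2.3 to 6.9. Total with the unvaccinated: 2.9 to 8.6, or 5% to 15% of 56.

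Hence about 1 to 9 cases at the planning rates.

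**4. Effect on crude effectiveness (true value 70%).** VE = 1 − [(39.5 + vaccinated carry-in)/13,156] ÷ [(17.9 + unvaccinated carry-in)/1,794]. Each range runs from L = 1 to L = 3.

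| Hazard at entry (assumed) | Vaccinated at own rate: cases; VE | Vaccinated at unvaccinated rate: cases; VE |
|---|---|---|
| As planned | 1.3 to 3.8; 70.4% to 71.2% | 2.9 to 8.6; 69.2% to 67.8% |
| Doubled | 2.5 to 7.6; 70.8% to 72.2% | 5.8 to 17.2; 68.5% to 66.0% |
| Five times | 6.3 to 19.0; 71.9% to 74.4% | 14.4 to 43.1; 66.6% to 62.0% |

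The direction differs between the two columns. For comparison, five cases all in one group would give 77% if unvaccinated (22.9/1,794 against 39.5/13,156) or 66% if vaccinated (17.9/1,794 against 44.5/13,156). Both the count of five and the one-sided split are assumptions.

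**5. What the count covers.** Step 3 counts every infection acquired but not yet diagnosed at entry, including silent incubation. Those already symptomatic or tested are only part of it. A diagnosis made before enrolment and reported as new in week 1 would come on top. The protocol allows neither part to be estimated.

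**The case against.** The strongest reply is that the protocol never says such cases will be counted. Sections 6.7 and 9.3.2 speak of new diagnoses and new infections, the first objective separates past from prospective infection, and Section 9.3 leaves analysis detail to a full SAP that is not shown. This stands as far as it goes. A reader might infer that infections acquired before entry are by design treated as incident; no passage supports that. A reader might also infer that follow-up starts before baseline; that is true of the order of forms only, since the start of person-time is not defined. A missing definition of time zero would by itself be SAP content and no finding.

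The reply does not cover form order and content, which the protocol fixes. An SAP cannot classify cases by onset or sample date if those dates were never collected. The Section 6.4 list may not be exhaustive, and the schedule's tick for MPX testing suggests that more is intended, but the two need to agree. Registry linkage (Sections 3.1 and 6.3.1) could supply some dates, but it is optional and needs further approval.

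Three further points stand. Reordering the forms does not detect silent incubation, which is missed in either order. If incidence is steady and cases are counted by diagnosis date, carry-in at entry is offset by infections still undiagnosed at the end, so overall incidence is not necessarily inflated; that offset does not protect effectiveness when entry coincides with vaccination. Finally, enrolling people with MPX is not a defect in itself, because baseline prevalence requires them.

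**Conclusion.** The point holds as a gap in data collection and case assignment: MPX already symptomatic or tested at entry can be counted as prospective incidence. It is worth correcting because the change is cheap and missing dates cannot be recovered reliably later.

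The likely size is modest. At the planning rates, carry-in is about 1 to 9 cases against 56, and crude effectiveness of 70% would read between about 68% and 71%. This rests on the assumed 1 to 3 week window, linear switching, and the planned hazard at entry. Larger shifts, such as 62% or 74%, require a hazard at entry five times higher. Recruitment at clinics and after exposure makes some increase plausible, but the protocol gives no figure for it. Neither a definite inflation of incidence nor a definite direction of bias in effectiveness can be claimed.

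**What to change.** - **Order.** Complete the baseline form before, or together with, the first weekly form.
- **Content.** Reconcile Section 6.4 with the schedule of assessment. At baseline, record any past MPX diagnosis with its date, current symptoms with onset date, and any pending MPX test. Add onset and sample dates to the Section 6.7 module.
- **Case rule, Section 9.3.2.** Count as incident only cases with both symptom onset and test sample after enrolment; assign the rest to baseline prevalence. This keeps infections that become apparent after post-exposure vaccination.
- **Sensitivity analysis.** Start person-time and events after a prespecified lead-in, with its length justified (21 days would be an assumption). Do not apply it to the post-exposure vaccination estimate, because it would remove the cases that estimate needs.

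Cost: reordering two forms, a few added items and some analysis wording. A 10 to 15 minute form at entry may lose a few enrolees. Holding 52-week person-time constant, a lead-in of 1 to 3 weeks corresponds to 14,949 × 52/51 = 15,242 up to 14,949 × 52/49 = 15,864 participants, or could be absorbed by the planned follow-up of up to 78 weeks.
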